7 INTRODUCTION

7.1 Background

We know that 1 in 4 people will experience a diagnosable mental health problem in any given year, and also that mental health problems represent the largest single cause of disability in the UK [1]. We also know that nearly one in three people with a long-term physical health condition also has a mental health problem [2], and that poor mental health costs the UK economy at least £117.9 billion annually [3].

Mental health conditions can have wide ranging negative impacts on individuals' lives and well-being. For instance, depression and anxiety disorders can lead to a range of adverse psychological, social, and employment outcomes [4]. Of those people with recognised mental health conditions, negative experiences with mental health services are commonly reported [5]. Nearly half of survey respondents (44%) who had received NHS therapies in 2019 reported that they had to wait too long to access them [5]. Long wait times to access mental health services can have significant health and economic impacts; a recent study by the Royal College of Psychiatrists found that 38% of people waiting for treatment reach out to crisis services and 11% go to A&E [6].

Demand for mental health services is currently outstripping capacity, and has increased significantly since the pandemic, with the Centre for Mental Health estimating that up to 10 million people, including 1.5 million children, are likely to need new or additional mental health support as a direct result of the crisis [7]

The NHS Long Term Plan aims to promote digitally enabled care, improve access to mental health support for 1.9 million people, and support NHS Trusts at meeting their referral key performance indicators [8]. Wysa's solution is well-placed to support these goals by providing an engaging and easy to access digital intervention approach that can be implemented from the point of self-referral. This is also aligned with NHSx's mission, particularly its aim to use digital technology to improve health and care productivity and empower people to access information and services to manage their own health [9].

7.2 Rationale

A key issue with current mental health service provision is lack of timely access to therapy or professional support. NHS talking therapies services are overwhelmed with high volumes of referrals, many of which are often inappropriate due to patients living out of area, or having very complex needs which are out of the scope of NHS talking therapies interventions. We predict that automations in the referral process brought about by the use of the Wysa electronic triage will result in significant administrative and clinical time savings, by enabling a large part of these assessments to take place via the app, and may also reduce the number of inappropriate referrals, due to users with complex needs or who are ineligible or at high risk being signposted to alternative services at an earlier stage. Our solution also enables immediate, guided support at the point of referral, thus enabling patients to manage their symptoms independently whilst waiting for treatment to begin. We know from our preliminary work that using the Wysa app at the onboarding stage is likely to result in improved outcomes for those who engage highly [10]. This research will also add to the findings of an ongoing RCT looking at the effectiveness of the Wysa app as a mental health support tool for NHS talking therapies patients waiting for therapy. When considering the application of AI to mental wellbeing, the ability to feel listened to is the most influential factor in patient satisfaction

Version number 1.1 - 25th November 2023

and response. Users need to feel able to share their thoughts with the AI and our user testimonials show that the anonymous nature of this text-based interaction is imperative to them, even though they know they are communicating with an AI chatbot.

Mental health services follow a stepped care model, with Step 1 being monitoring by the GP, and Steps 2-4 reflecting more intensive interventions as clinical need increases. Step 2 services typically support mild to moderate mental health conditions, while Steps 3 and 4 involve other specialised treatments for more severe or complex conditions. Whilst cCBT and guided self-help are recognised treatment options at step two, a lack of available trained therapists to assess and treat a growing demand means that there are often significant waits before these interventions are offered. Our therapist enabled cCBT solution aims to provide an alternative way of meeting some of this demand, allowing a significant proportion of the therapeutic intervention to take place via the app, at a time and a place that is convenient for the service user.

The Wysa AI and therapist assisted cCBT programmes are unique in that the programmes offer 24/7 continuous conversational care throughout the patient treatment journey, in addition to weekly psychoeducational videos, practice of specific CBT techniques through conversations with the Wysa chatbot, and daily engagement via push notifications. The programmes aim to keep the user engaged whilst learning to manage their symptoms. The treating therapist will review and guide the patient biweekly or monthly, thus allowing the patient to address any difficulties they have with any concepts/ tasks. We hope the findings from this research will add to the findings of a pilot study by Leo et al (2022), which found that users with pain related impairment who completed an 8 week Wysa digital mental health intervention as part of their orthopaedic care showed greater improvement in depression, pain interference, and physical function than patients who received usual orthopaedic care only [11].

This solution also has the potential to reduce inequalities in service provision, and is especially important for individuals from high risk groups (such as LGBTQ+ or Black and minority ethnic groups) who are least likely to seek or receive support for their symptoms [12,13]

Implementing automated support and treatment has the potential to reduce face-to-face appointments. If this is borne out, it would contribute to a reduction in the demand for travel whilst also reducing the demand of building spaces, contributing to the NHS's Net Zero Carbon goal [14]. Early interventions also have the potential to prevent further ill health, which would result in less demand, when symptoms are more chronic, often for more specialised services.

7.3 Research Question

The main research question of the study is: What are the benefits of adopting Wysa therapeutics for patients, clinicians, services and the wider health care system?

7.4 Aims and Objectives

The primary aim of this project is to understand the clinical benefits of Wysa AI therapeutics for patients.

The Primary objective of this study is as follows:

- Do Wysa therapeutics (e-triage, self-help tools & conversational care; guided cCBT), when deployed at referral, waitlist, and intervention, improve clinical outcomes?

The Secondary objectives of this study are to explore:

- Do Wysa therapeutics improve service referral rates and/or reduce drop outs or DNAs?
- Do Wysa therapeutics improve patients' quality of life?
- Do Wysa therapeutics have an impact on waitlist numbers or other service related resources?

[figure not shown]

Figure 2: Wisconsin Logic Diagram

8 METHODS

8.1 Study Design

A quantitative evaluation will be used to understand the impact of Wysa's application at key points in the patients' care pathway:

- At referral
- Whilst waiting for treatment
- As an intervention

The evaluation will include an analysis of app usage data and clinical outcome data, in order to establish engagement levels with Wysa therapeutics, as well as Wysa's efficacy at improving mental health outcomes.

The study will be comprised of two parts:

Part One: Evaluation of Wysa e-triage

Part Two: Evaluation of Wysa self-help tools as waiting list support and Wysa cCBT programmes

[figure not shown]

Figure 3: Participant flow Diagram

8.1.1 Timeline

The study will last for 10 months: 3 months of evaluation, refinement and technical integration, 6 months of data collection (the total time period for each participant journey will be approximately 20 weeks, thus allowing a 4 week onboarding window), and 1 month of post-evaluation analysis and preparation for dissemination.

8.2 Study Context

8.2.1 Participants

The target population of the study will include patients who are 16+ who are referred, or self-refer to NHS talking therapies adult mental health services for support, and who at any stage of their NHS talking therapies journey, download and use any of the Wysa functionality.

The cCBT programmes will be accessed by a subset of the patients who are accepted for step 2 treatment. Step 2 treatment is usually offered to patients experiencing mild or moderate depression and/ or anxiety symptoms as recommended by NICE guidelines for stepped care in NHS talking therapies services.

8.2.2 Setting

Participants will be recruited by NHS talking therapies services where we have worked collaboratively to design and trial the use of Wysa therapeutics in the care pathway.

The Wysa interventions are accessible to users through either a web widget or a mobile phone app available on android and apple.

8.2.3 Interventions

Wysa therapeutics include;

- An electronic triage, comprising of two parts:
 - a referral triage, comprising demographic information and some limited questions around physical health and past contact with mental health services
 - a clinical assessment triage, comprising a wide range of clinical questions and standardised outcome measures.
- Waitlist support;
 - 24/7 conversational care,
 - Access to over 150 self care tools
 - Daily check-ins to increase engagement and promote behavioural change.
- A range of diagnosis specific, NICE compliant therapist enabled step 2 cCBT programmes, delivered to patients via an app or widget. Each programme consists of 6-8 weekly modules, with each module focussing on a specific CBT principle or intervention. Psychoeducation is provided through short videos, with CBT techniques introduced in each video practised through conversational AI and augmented with self care audios and editable worksheets. The programmes also include the collection of standardised NHS talking therapies clinical outcome measures.

Wysa is delivered as a standalone system which patients download directly onto their personal device. Upon e-triage self-referral or alternative route referral to NHS talking therapies services the individual is automatically sent a download link via sms, email or QR code. Once downloaded, data from within the app, including outcome measures, tools used and crisis alerts are automatically pushed to the electronic patient record (iaptus) using the Mayden Prism software.

8.2.4 Outcomes

8.2.4.1 Primary Outcomes

In order to understand the impact of Wysa therapeutics across the care pathway we will be conducting two distinct analyses. In Part 1 we will be focusing on e-triage and in Part 2 we will be focussing on the waitlist support and cCBT programmes.

The primary analysis in Part 1 will be a comparison of the time spent by the clinician to make a decision on the treatment pathway for those who complete the Wysa e-triage, with that taken to make a decision for patients who do not. The primary outcome measure will be time taken for the clinician to make a decision, for each of these two assessment pathways.

The primary analysis in Part 2 will be a comparison of depression and anxiety scores before and after a Wysa intervention (waitlist self care or step 2 cCBT). The primary outcomes will be measured at onboarding, start of intervention and discharge from intervention. In line with the national recommendations laid out by the NHS talking therapies Manual, we will be using Wysa's AI automation to encourage users to complete the Patient Health Questionnaire (PHQ-9 [15) and General Anxiety Disorder (GAD-7 [16]) routine outcome measures.

	Primary Outcome	Outcome Measure
Part 1: E-triage	Clinical Time Savings	Hours/Minutes
Part 2: Waitlist and cCBT	Depression or Anxiety severity	Score on the PHQ9 and GAD7

Table 5. Primary Outcome Measurement

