5 STUDY SUMMARY

Table 3. Study Summary

Study Title	The benefits of adopting WYSA therapeutics for patients, clinicians, services and the wider health care system.	
Short title	An evaluation of Wysa therapeutics	
Study Design	The study proposed is a real world quantitative evaluation to investigate the impact of Wysa therapeutics on clinical outcomes, and the experience of using the products in people with mild to moderate common mental health disorders. Outcome measures will include client satisfaction questionnaires and PHQ9 and GAD7 scores, as well as clinical and/or administrative time savings.	
Study Participants	The target population of the will include individuals over the age of 16 years who are referred, or self-refer, to Improving Access to Psychological Therapies programme (NHS talking therapies) for mental health support.	
Planned Size of Sample	The planned sample size is 100 individuals from 5 provider sites, two run by Dorset University Healthcare NHS Foundation Trust and three run by Lanchashire and South Cumbria NHS Foundation Trust.	
Follow up duration	N/A	
Planned Study Period	The study will last 18 months which includes three months of evaluation refinement, ethical approval, technical integration and testing. A further three months will be required for analysis of some secondary outcomes and preparation for dissemination.	
Research Question/Aim(s)	 The study aims are as follows: 1. To establish real-world evidence of the effectiveness of Wysa as a referral and triage tool. 2. To establish the impact of Wysa as a self help mental health support tool for patients waiting for treatment. 3. To establish the effectiveness of therapist enabled Wysa cCBT interventions on mental health outcomes. 4. To evaluate user experience of the range of Wysa therapeutics. 5. To establish if the adoption of Wysa therapeutics results in any service related efficiencies, for example clinical or administrative time savings. 	

The main research question is: How do the range of Wysa therapeutic tools benefit patients, clinicians, services and the wider health care system?
health care system?

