From here the patient will be offered the opportunity to download the Wysa app as a waitlist support tool until they are offered an intervention. The Wysa app includes over 150 self care tools, conversational AI and daily check-ins and reminders via push notifications. We will analyse data collected from within the app to understand app usage and any effect use of the app may have on mental wellbeing markers during the wait period.

Patients who are then offered Wysa's cCBT by their assessing clinician will have access to diagnosis specific weekly web or app based programmes including psychoeducational videos and CBT conversational techniques, as well as periodic reviews by an NHS talking therapies clinician through a communication dashboard called the Therapist Companion, which is also fully integrated into the service EPR system. We will report on changes in clinical outcome measures and engagement metrics to understand the efficacy of these cCBT programmes.

For all patients using Wysa within the service there is a built in SOS response. Wysa has three pathways to crisis alert and response:

- Patients are able to trigger crisis help by selecting the 'SOS' button on the app.

Version number 1.1 - 25th November 2023

- Crisis response will be triggered by responses to PHQ9 question 9
- Crisis response will be triggered when risk language is used (and confirmed by the chatbot) within free text.

When Wysa or the user triggers the crisis response pathway, users will be offered to complete a safety plan, engage in grounding exercises, and be provided with local or national crisis helplines. We will collect data including the number of times that the Wysa SOS response is triggered, the number of false positives identified by the AI, and SOS tool usage.

After patients have been discharged, Wysa can also be used as a support/ relapse prevention tool. All participants will have access to the AI Chatbot and self tools for 12 months from onboarding.

[figure not shown]

Figure 1. Current NHS talking therapies care pathway flows including Wysa therapeutics.

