8.3.2 Sampling

8.3.2.1 Sample Size

All patients accepted by the NHS talking therapies services and meeting the inclusion criteria will be eligible for the study. A minimum of 100 patients will be recruited in order for the study to be able to conclude statistical validity. This is primarily a quantitative feasibility review with no control arm.

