10 DISSEMINATION POLICY

10.1 Dissemination Strategy

Analysis of the data will be compiled into a published peer-reviewed paper. This data will also be used to support MHRA Class IIa regulatory approval and wider adoption practices.

The national framework for NHS talking therapies services outlines the referral and assessment pathway. WYSA has been designed to align with NHS talking therapies guidelines including minimum dataset requirements. Strong relationships across the AHSN network and central NHSX will be used to disseminate the results and gain support for further deployments.

Interoperability with digital systems is an important element of this real-world evaluation study. The API integration with Mayden Prism software is an important part of our current and proposed work streams, as it supports easy integration with existing systems and facilitates the incorporation of Wysa into existing care pathways. NHS talking therapiesus is currently one of two leading patient management systems for UK NHS talking therapies services, which will allow for rapid technical deployment following the results of this study.

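### The Part 2 primary analysis is an uncontrolled before-after comparison, yet the protocol reads it as effectiveness; regression to the mean and natural recovery would count as Wysa benefit

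*Protocol*

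**What the plan says.** Section 8.2.4.1 of the protocol fixes the contrast: "The primary analysis in Part 2 will be a comparison of depression and anxiety scores before and after a Wysa intervention". It covers waitlist self care or step 2 cCBT, and the timing is given as "The primary outcomes will be measured at onboarding, start of intervention and discharge from intervention". No comparison group is named. The Part 1 primary analysis in the same section does have one, namely patients who do not complete the e-triage.

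Section 8.3.2.1 adds "This is primarily a quantitative feasibility review with no control arm". Section 8.2.1 defines the target population as people who download and use some Wysa function.

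The result is meant to carry more than description:

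- Section 5, third aim: "To establish the effectiveness of therapist enabled Wysa cCBT interventions on mental health outcomes".
- Section 6: score changes are reported "to understand the efficacy of these cCBT programmes".
- Section 7.4: the primary objective asks whether Wysa improves clinical outcomes.
- Section 8.1: the evaluation is to establish Wysa's efficacy.
- Section 10.1: "This data will also be used to support MHRA Class IIa regulatory approval".

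Sections 6 and 8.5 also announce a comparison of Wysa users with non-users. They do not say that it is the Part 2 primary analysis, where non-users' scores come from, or how the groups would be adjusted. Section 8.6 lists only device access and language as limitations.

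**The concern.** People refer themselves, or are referred, when symptoms are bad enough to seek help. Scores taken at such a point tend to be above the patient's usual level and to drift down on remeasurement. Some patients also recover over the follow-up, which section 8.1.1 describes as "the total time period for each participant journey will be approximately 20 weeks". A within-patient comparison attributes both movements to whatever was used in the interval.

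A significant before-after fall is therefore not evidence for the primary objective as worded. The test may hold its error rate for the question of whether scores changed, but not for the question of whether Wysa changed them. The second question is the one in the aims, and the data are also intended to support a regulatory submission.

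**Working it through.** **The plan's own figure.** Section 8.3.2.1 says "A minimum of 100 patients will be recruited in order for the study to be able to conclude statistical validity". It gives no significance level, power, effect size, SD or dropout, so the 100 can be neither reproduced nor refuted. It is used below only as the number of pairs.

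**Inputs.** From the protocol: n = 100. Assumed: score SD 5.5 at both times; baseline mean 2 to 4 points (the gap) above the mean to which scores regress; test-retest correlation r of 0.5 to 0.8; no Wysa effect; paired t-test, two-sided 5%, hence 2.5% in the direction of improvement.

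**Formulas.** Expected fall = (1 − r) × gap. SD of change = 5.5 × √(2(1 − r)). Standard error = SD of change / √100. The chance of a significant improvement is approximately Φ(fall/SE − 1.96). The table gives paired t-test values, which agree with this to within about 0.01.

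| Gap | r | Fall | SD of change | Fall/SE | Chance |
|---|---|---|---|---|---|
| 2 | 0.5 | 1.0 | 5.50 | 1.82 | 0.44 |
| 2 | 0.8 | 0.4 | 3.48 | 1.15 | 0.21 |
| 4 | 0.5 | 2.0 | 5.50 | 3.64 | 0.95 |
| 4 | 0.6 | 1.6 | 4.92 | 3.25 | 0.90 |
| 4 | 0.8 | 0.8 | 3.48 | 2.30 | 0.63 |

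As a check on the second row, Φ(1.15 − 1.96) = Φ(−0.81) = 0.21. Section 8.2.1 says that only a subset of step 2 patients will use cCBT, so that phase may have fewer pairs. With 50 pairs the range is 12% to 71%.

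**A second model.** Suppose patients enter only above a cut in a normal source population. Then fall = (1 − r) × SD × λ, where λ is the inverse Mills ratio at the cut. Take SD 5 to 6, r 0.6 to 0.9, and a cut at the mean or 0.5 SD above it.

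- Lowest case: 0.1 × 5 × 0.798 = 0.40 points. With SD of change 2.20, Φ(0.40/0.22 − 1.96) = 0.44.
- Highest case: 0.4 × 6 × 1.141 = 2.74 points. With SD of change 4.96, the chance is above 0.99.

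**Natural recovery alone.** An assumed mean recovery of 1 to 2 points with SD of change 5 to 6 gives 0.39 to 0.98 with 100 pairs.

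**What a comparator would need.** Per group, n = 2(1.96 + 0.84)² × SD²/difference² for 80% power at two-sided 5%. For a 2-point difference this is 99 (SD 5) to 142 (SD 6). A total of 100 split equally has power 0.52 to 0.39. These SDs are also assumed.

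**The case against.** **It is a feasibility review.** Sections 6 and 8.3.2.1 say so, and a before-after summary is acceptable for that purpose. This stands. The fault lies in the effectiveness and efficacy reading, not in computing the change.

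**A comparison with non-users is planned.** Sections 6 and 8.5 do announce one, so it would be wrong to say that the study contains no contrast at all. But section 8.2.4.1 defines the Part 2 primary analysis without it, and it conflicts with the users-only population of section 8.2.1 and the absence of a control arm in section 8.3.2.1.

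**A statistical analysis plan may settle it.** A SAP can add adjustment and detail. Here the protocol itself fixes both the primary contrast and the claims drawn from it.

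**The numbers are assumed.** They are, and the protocol names neither a test nor a significance level. The figures show what the design allows and do not predict the result.

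Some stronger readings are tempting, but the documents do not support them:

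- *Therapist contact confounds the cCBT result.* The third aim concerns a therapist-enabled product, and section 7.2 makes therapist review part of it. Review need not be separated from the app to address that aim.
- *The waitlist and cCBT phases are pooled.* Section 8.2.4.1 and Table 5 treat them together loosely. But the three measurement times allow phase-specific contrasts, the aims are separate, and nothing states that the phases will be pooled.
- *Regulatory approval would rest on the before-after result alone.* Section 10.1 says only that the data will support it.

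**Conclusion.** The concern holds. As written, the Part 2 primary analysis cannot distinguish a Wysa effect from regression to the mean or natural recovery, while the aims and the intended regulatory use treat the result as evidence of benefit. The limitations section does not mention this.

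The size is illustrative. With no Wysa effect, the first model gives a fall of 0.4 to 2.0 points and a 21% to 95% chance of a significant improvement with 100 pairs, against 2.5%. A reader might infer that a spurious significant fall is likely in every case. The lower end of the range does not support that, although even 21% is about eight times 2.5%. The conclusion itself needs none of these figures; it follows from the missing comparator and the wording of the claims.

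**What to change.** 1. Reconcile sections 6, 8.2.1, 8.2.4.1, 8.3.2.1 and 8.5 on whether non-users are in the study and which analysis uses them.
2. Report before-after change in PHQ-9 and GAD-7 as descriptive within-person change, separately for onboarding to start of intervention (waitlist app) and start of intervention to discharge (cCBT).
3. In sections 5, 6 and 8.1, replace effectiveness and efficacy with change during use wherever no comparator is used.
4. Add the missing control, regression to the mean and natural recovery to section 8.6.
5. Where routine scores of concurrent non-users are available under the study's data permissions, base any effectiveness statement on the user versus non-user comparison already announced. Adjust for phase-specific baseline score, time since referral and site. Label it observational, with residual self-selection and limited precision.

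Items 1 to 4 cost protocol wording and a more modest headline claim. Item 5 is conditional. Section 8.4.1 collects study measures at e-triage or app onboarding and then in the app, and section 8.3.3.2 gives data-use information on download, so the protocol shows no source of onboarding or waiting-period scores for people who never use Wysa. Section 6 offers Wysa to everyone with a suitable device, so non-users have declined it or lack a device. Adjustment would not remove that selection.
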